## STUDY PROCEDURES

		Visit 1	Visit 2 (within 4 months after V1)
FDRs	MRI positive	Vitals MRI Blood draw Environmental Questionnaire NeuroQOL SDMT Activity Questionnaire Diet questionnaire	Blood draw
	MRI negative Controls	Vitals MRI Blood draw Environmental Questionnaire NeuroQOL SDMT Activity Questionnaire Diet questionnaire	Blood draw
	MRI negative Non-Controls	Vitals MRI Blood draw Environmental Questionnaire NeuroQOL SDMT Activity Questionnaire Diet questionnaire	
NonFDR Controls		N/A	Vitals Blood draw Environmental Questionnaire NeuroQOL SDMT Activity Questionnaire Diet questionnaire

### D. Description, Risks and Justification of Procedures and Data Collection Tools:

1. Blood Draws: The risks of phlebotomy are small and include temporary discomfort from the needle stick, bruising and rarely infection. The amount of blood drawn at each time point for this study is well under the established recommended maximum for adults.
2. MRI: The most common side effect of having an MRI is flashing lights in the eyes. This is caused by the magnetic waves and is not harmful. Some people also experience warmth and reddening of the skin. This usually goes away in a few minutes. This is a NON-contrast scan. In addition, there is an emotional risk of identifying abnormal MRI lesions in individuals with no symptoms concerning for MS, and an as-yet unknown risk of developing symptom concerning for, or disability related to, MS. This potential risk should be offset by the potential benefit of earliest possible intervention for a potentially disabling disorder.
3. Confidentiality: There is a potential for loss of confidentiality. A unique study number will be assigned to each subject at inclusion, immediately after informed consent has been obtained. This number will serve as the subject's identifier. Link between study number and subject's identity will be kept separately from study data on a secure server accessible only to study personnel. Data will be stored in a HIPAA-compliant database.

## **E. Potential Scientific Problems:**

The largest potential hurdle would be inadequate numbers of FDRs with positive brain MRIs. That said, we view this cross-sectional study as a proof of concept that patients can be recruited, and that we can develop a biobank of specimens to be interrogated in the future. The long-term goal is creation of a longitudinal, multi-center study similar to the DAISY study of children at increased risk for T1D. Thus, we have no illusion that we will settle this issue with a relatively small cross-sectional study, but plan to use this study to lay the groundwork for a larger, longitudinal study, especially recruiting at other national/international sites.

## **F. Data Analysis Plan: Statistical Approach**

- a. Based on previous studies, we estimate that 5-10% of the 300 FDRs (15-30) in our pilot study will exhibit an MRI endpoint. In order to test for associations with this endpoint to obtain valuable preliminary data, we will perform a nested case control study. We will match two controls per case based on age and sex: one group will be FDRs not fulfilling DIS on brain MRI; the second will be non-FDRs who are age- and sex-matched to FDRs who do, and do not, fulfill DIS on MRI scans. The non-FDRs will perform the environmental screen and undergo venipuncture for blood analysis identical to the other two groups, but will not have a MRI scan.
- b. Aim 1. Descriptive statistics
- c. Aim 2. Association analyses; with individual factors and in a multiple risk factor analysis. In previous studies, HLA type, Vitamin D levels, Epstein Barr Virus exposure, smoking and early adult obesity have conferred a maximum odds ratio of 2-3 (many SNPs confer an odds ratio of 1.1-1.4) of developing MS when studied individually. In the GEMS study, participants were stratified into high and low risk categories based on a deep phenotyping of 64 SNPs, and environmental screen (including sex). Comparative analyses were performed on the high and low risk groups for both neurological exam and MRI measures. In this study, we plan to use the known risk factors, and add potential biomarkers (e.g. NfL, lipid levels) to define the risk of DIS in this population. For the power analysis we made the assumption that no single marker would exhibit an odds ratio greater than 2 for increased risk of DIS, and that all markers are additive. In this early proof of concept phase, with an estimated case sample size of 30 with 60 age- and sex-matched controls, our priori power analysis suggests an expected power ranging from 20-33% for risk factors such as smoking, obesity, and vitamin D deficiency. Using frequency and odds ratio from the GEMS study (OR = 2.9) we expect a power of 64% to detect an effect of HLA type risk. While this study will be statistically underpowered, and estimates will be imprecise, we expect that some results will have clinical significance. We plan to use these results and stored samples as the groundwork for larger, longitudinal, multi-site studies. These future studies will allow us to enroll samples sizes of greater than 500, necessary to reach 80-90% power. In reality, it is possible the effect some factors may depend on the levels of other factors. Example hypothesis that we will test: FDRs with DIS lesions are more likely to have been exposed to EBV as indicated by elevated EBV serology than FDRs of the same age and sex without DIS lesions. By extension, we will then define a risk score combining factors that are discriminatory, e.g. Vitamin D level, smoking, obesity, elevated NfL levels, impaired B cell anergy, and HLA type may each have a roughly 2 fold increased risk, whereas those with four of these factors have a six-fold increased risk of DIS on MRI.
- d. Aims 3 and 4 do not have statistical implications.

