The sequences were specifically chosen to: a) screen brain with the greatest specificity (FLAIR\*); b) allow for later volumetric analysis of the brain; and c) use the most sensitive technique for cortical and subcortical brain lesions (3D-DIR).

**B. Description of Population to be Enrolled:** The population will be a total of 300 women and men, of all races and ethnicities, between the ages of 18-30, inclusive, who have no symptoms of MS, but have at least one FDR with documented MS fulfilling McDonald 2017 criteria. Up to 1000 will be screened for inclusion, but some will be excluded due to inability to undergo a brain/spine MRI or have blood drawn, lack of interest after discussion of study requirements, or symptoms concerning for MS (the latter will be referred to a qualified neurologist for evaluation). FDRs with one or more siblings/parents with MS will be included, and more than one FDR of a proband MS patient will be allowed. A control group (based on # of FDRs with positive MRIs - we anticipate 15-30) of age- and sex-matched controls who have no known family members with MS (out to first cousins and grandparents) will have blood drawn and fill out the environmental questionnaire, but will not undergo a brain MRI. The controls will be matched 1:1:1 for those FDRs with positive MRI scans suggesting pre-symptomatic MS and those age-and sex-matched FDRs who do NOT have positive MRI scans suggesting pre-symptomatic MS. The ages were specifically chosen so as to have a good opportunity to collect an adequate number of MRI-positive, asymptomatic participants prior to the known median age of MS clinical onset (30 years), but not so young as to lower the likelihood of detecting asymptomatic brain MRI lesions.

1. FDR Inclusion Criteria
  - a. Male and female
  - b. All races and ethnicities
  - c. Ages 18-30
  - d. Must have a parent, sibling or child with MS fulfilling McDonald 2017 criteria
  - e. No symptoms suggestive of MS on formal screen
  - f. Ability to undergo a non-contrast MRI and venipuncture, and perform an environmental screen, mood screen and cognitive test
2. FDR Exclusion Criteria
  - a. Symptoms suggestive of MS on formal screen
  - b. Prior diagnosis of autoimmune disease that may be associated with CNS dysfunction and MRI lesions, e.g. Sjogren's
3. Non-FDR Inclusion Criteria
  - a. Male and female
  - b. All races and ethnicities
  - c. Ages 18-30

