### **C. Study Design and Research Methods:**

1. Prescreen FDRs by phone for ability to participate and lack of MS symptoms, using a standardized script to exclude those with overt MS symptoms. Proband MS patients will have documented MS by McDonald 2017 criteria.
2. Qualified FDRs will be scheduled for a study visit after completing a pre-screening questionnaire by phone. If they are not excluded by pre-screen, and wish to participate, a study visit will be scheduled. A waiver of documentation of consent will be obtained over the phone so as to instruct participants to fast from midnight prior to the first study visit. This will also allow them to fill out the environmental questionnaire on-line before their visit and at their convenience. The environmental survey must be completed at least three days prior to their visit. If not, the study visit will be canceled and rescheduled once its complete.
3. A study visit will include (See Table of activities below):
  - a. Read, ask questions regarding, and sign the consent.
  - b. Document completion of environmental questionnaire.
  - c. Obtain a measured height and weight, and compute a Body Mass Index (BMI)
  - d. Perform a non-contrast brain MRI (per section V.A)

- e. Perform a fasting Blood draw consisting of no more than 100 ccs of blood.
  - i. Blood drawn at the primary study visit will be a maximum of 100 ccs to be processed in the following fashion. Participants will not be made aware of their blood sample results
    - 1. 30 ccs for immediate cell sort by [name] into T and B lymphocytes, for CD40 expression studies, requiring primary analysis with fresh cells, and done on all samples. Also for HLA analysis.
    - 2. 20 ccs processed for delayed analysis of SNPs, viral serologies (Herpes Simplex Virus 1 and 2, Cytomegalovirus, Varicella-Zoster Virus, and Epstein-Barr Virus), vitamin D levels, and neuroaxonal (NfL - Quanterix) and myelin damage (lipids), which all can be performed on stored samples.
    - 3. 50 ccs processed and stored for delayed analysis of plasma and PBMCs, RNA and DNA, for studies not yet determined
- f. Perform the Perceived Stress Scale and the Neuro-QoL screen for anxiety and depression;
  - i. Participants screening for concerns for suicidality on the mood screen will be referred to an emergency room for evaluation.
- g. Perform a Symbol Digit Modality Test, a screen for cognitive function. The latter will be done in the written format.

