  - i. Participants will not be advised of Cognitive screen results.
- h. As a measure of physical activity, we will use Godin Leisure-Time Exercise Questionnaire (GLTEQ), which measures mild, moderate and strenuous physical activity during a typical seven day period. This has been validated in MS, and is scored either into three levels of activity (sedentary, moderately active, or active), or may be used as a continuous measure.
- i. As a dietary assessment, we will use the Harvard 2007 Booklet FFQ, which is a semi-qualitative food frequency questionnaire used to assess intake of various nutrients over the past year. This has been robustly validated in a variety of populations, and nutrient intakes are computed by assigning a daily frequency weight.

4. MRIs will be read by a board-certified neuroradiologist ([name]) with extensive experience in reading brain MRIs in general, and MS MRIs in particular. All FDRs will receive a follow-up contact concerning the results of their MRI within one week. FDRs with a brain MRI fulfilling criteria for DIS will be referred to a qualified neurologist to determine if they should be treated or monitored more closely. Individuals with abnormal brain MRI scans not suggestive of or fulfilling DIS criteria, but having non-specific brain lesions (as can be seen with migraine and many other conditions), also will be referred to a qualified neurologist for evaluation as needed. Those FDRs with unexpected abnormalities (e.g. severe sinus disease, pineal cyst, pituitary abnormality, cavernous angioma, etc.) will be referred as necessary to a qualified physician.

5. FDRs with a positive brain MRI showing lesions DIS will be asked to return within four months for a repeat blood draw of no greater than 100 cc of blood, to be compared to age-and sex-matched FDRs without a positive brain MRI (who will also be asked to return within 4 months for the repeat blood draw) and age-and sex-matched non-FDRs, both in a 1:1 ratio. The former will be identified from those already in the study, and the latter will be recruited from age- and sex-matched friends of the FDRs with positive brain MRIs. The non-FDRs will be prescreened and perform all the study procedures as the FDRs on the first study visit, with the exception of the MRI.

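### For factors already measured in every scanned FDR, the Aim 2 comparison uses one matched DIS-negative FDR per case and leaves about 240 to 270 others out

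*Combined protocol and SAP*

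**What the plan says.** Section V.F, item a, expects 15 to 30 of the 300 FDRs to meet the MRI endpoint and then sets the design: "In order to test for associations with this endpoint to obtain valuable preliminary data, we will perform a nested case control study". It continues: "We will match two controls per case based on age and sex: one group will be FDRs not fulfilling DIS on brain MRI". The second control group is non-FDRs, who give blood and complete the environmental screen "but will not have a MRI scan".

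Other sections agree on the ratio. Section V.B says "The controls will be matched 1:1:1 for those FDRs with positive MRI scans". Section V.C, item 5, describes 1:1 matching to each control group and says of the DIS-negative FDR controls: "The former will be identified from those already in the study". They are therefore drawn from people already scanned and measured.

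The Study Procedures table gives the remaining DIS-negative FDRs their own row, "MRI negative Non-Controls", with the same Visit 1 procedures as the cases and the selected FDR controls. Section V.C, item 3.e, describes blood taken at that visit "for CD40 expression studies, requiring primary analysis with fresh cells, and done on all samples".

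Section V.F, item c, rests its power statement on 30 cases and 60 matched controls: 20–33% for single factors with an odds ratio of at most 2, and 64% for HLA type with an odds ratio of 2.9.

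**The concern.** Sampling controls from a cohort is sensible when the exposure is costly to measure. The plan has such a case: B cell anergy and cytokines need fresh cells and are limited to the Visit 2 subset (V.C, item 5.a). For factors already recorded on all 300 FDRs, sampling saves nothing and discards information.

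The point covers obesity, activity, diet, mood, SDMT and CD40, and smoking if the environmental questionnaire records it. It does not cover HLA, SNPs, viral serologies (including the plan's EBV example), vitamin D, NfL or lipids unless these are run on all FDRs; for the stored-sample assays the plan says only that they can be done later. Nor does it cover B cell anergy, cytokines, or any risk score that includes them.

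What is at stake is the precision of the estimates. Section V.F, item c, offers the results as groundwork for larger studies, so intervals wider than the data require reduce what the pilot hands on.

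**Working it through.** **Inputs from the documents.** 300 FDRs, 15 to 30 cases, one DIS-negative FDR and one non-FDR per case (V.F.a, V.B, V.C.5); odds ratio at most 2 for a single marker (V.F.c). **Assumed, because not given:** two-sided 5% level and exposure frequency p0 in controls. All figures ignore matching and adjustment for age, sex and family.

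**1. FDRs left out of the within-FDR contrast**
- 30 cases: 300 − 30 − 30 = 240
- 15 cases: 300 − 15 − 15 = 270

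Using everyone gives 30 v 270 instead of 30 v 30, or 15 v 285 instead of 15 v 15.

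**2. The plan's own power figures.** I used a two-proportion test with pooled null variance and case exposure p1 = OR·p0 / (1 − p0 + OR·p0). For 30 v 60 and OR 2, power is 20% at p0 of about 9% and 33% at about 30%. For OR 2.9 it is 64% at p0 of about 27.5% or 42%. The stated figures can thus be matched only by back-solving for exposure, and they fit 30 cases against all 60 controls pooled. Under 1:1:1, 30 of those 60 are unscanned non-FDRs, so the stated power does not describe the within-FDR contrast.

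**3. Continuous measures (no exposure assumption).** SE in SD units = √(1/n1 + 1/n0). Equivalent equal group size = 2 / (1/n1 + 1/n0). Half-width and detectable difference are from the two-sample t test.

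| Cases v DIS-negative FDRs | SE | 95% half-width | Detectable at 80% power | Equivalent equal groups |
|---|---|---|---|---|
| 30 v 30 | 0.258 | 0.52 SD | 0.74 SD | 30 v 30 |
| 30 v 270 | 0.192 | 0.38 SD | 0.54 SD | 54 v 54 |
| 15 v 15 | 0.365 | 0.75 SD | 1.06 SD | 15 v 15 |
| 15 v 285 | 0.265 | 0.52 SD | 0.745 SD | 28.5 v 28.5 |

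**4. Binary factors, interval width.** SE(log OR) = √[1/(n1·p1(1−p1)) + 1/(n0·p0(1−p0))]. At p0 = 0.30 and OR 2, p1 = 0.6/1.3 = 0.4615.
- 30 v 30: SE 0.541, 95% CI 0.69–5.78
- 30 v 270: SE 0.390, 95% CI 0.93–4.29
- 15 v 15: SE 0.765, 95% CI 0.45–8.96
- 15 v 285: SE 0.534, 95% CI 0.70–5.69

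On the log scale the interval is 33% narrower at 10% exposure, falling to 19% at 80%, with 30 cases. With 15 cases the range is 36% to 20%.

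**5. Binary factors, power at OR 2.** The first figure in each cell is the two-proportion formula. The second is exact enumeration of the unadjusted logistic likelihood-ratio test.

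| Exposure | 30 v 30 | 30 v 270 | 15 v 15 | 15 v 285 |
|---|---|---|---|---|
| 10% | 15% / 17% | 32% / 26% | 10% / 14% | 23% / 16% |
| 30% | 25% / 26% | 44% / 42% | 15% / 15% | 28% / 26% |
| 50% | 26% / 26% | 41% / 42% | 15% / 15% | 23% / 25% |
| 80% | 16% / 18% | 17% / 25% | 10% / 14% | 8% / 17% |

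The two methods agree at middling exposures and differ at the extremes. At 10% exposure the formula overstates the gain; at 80% it understates it.

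**The case against.** - **Pilot status.** Sections V.E and V.F.c already call the study a proof of concept, underpowered and imprecise. On the figures above, power at OR 2 stays below 45% and the interval at 30% exposure still includes 1. This is true, and the number of cases remains the main limit. But accepting imprecision is not a reason to set aside data already collected.
- **Scope.** Most of the markers named in V.F.c for the risk score, and the EBV example, fall outside the point unless assayed in everyone. This stands, and it limits the recommendation to Visit 1 measures and CD40.
- **Left out of what?** The non-control FDRs still count in the Aim 1 prevalence and the Aim 4 biobank. This is correct; they are left out only of the Aim 2 within-FDR contrast.
- **Other wording.** Section III (Innovation, item d) promises to compare FDRs with and without MRI abnormalities and mentions no matching. V.C.6 calls the analysis case-cohort. However, item d specifies no full-cohort analysis, and V.C.6 refers back to the controls already described and defines no subcohort. Nothing assigns the non-control FDRs to an association analysis.
- **One common set.** Keeping the same matched people for Visit 1 and Visit 2 markers helps a combined score. This is a fair reason to retain the matched sets for that score, but not to restrict single-factor analyses.
- **Power depends on the test.** This stands. The interval widths and the continuous-measure figures are the firmer basis.

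**Conclusion.** The concern holds. For factors measured in every scanned FDR, the planned within-FDR contrast gives up precision at no saving. If 300 FDRs enrol and 5–10% are DIS-positive, using all of them makes the standard error of a mean difference about 25% smaller with 30 cases (0.258 to 0.192) and 27% smaller with 15 (0.365 to 0.265). That is like having 54 v 54 instead of 30 v 30, or 28.5 v 28.5 instead of 15 v 15. For binary factors the log-odds-ratio interval is roughly a fifth to a third narrower across assumed exposures of 10–80%; the power gain varies with exposure and test and can be negligible for common exposures. Age, sex and family adjustment and a small-sample correction would alter these figures and have not been modelled. This is a worthwhile improvement to the analysis; it does not make the study adequately powered.

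**What to change.** Add to V.F, item c, wording such as:

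> For each factor measured in all scanned FDRs at Visit 1, the primary within-FDR Aim 2 analysis is a logistic regression of DIS on the factor in all scanned FDRs, adjusted for age and sex. It uses a small-sample (for example Firth-type) method, given 15–30 events, and allows for several FDRs per proband.

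The last clause is needed because V.B permits more than one FDR per proband.

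Keep the matched sets for the Visit 2 assays, any score that includes them, assays run only on the subset, and the separate non-FDR comparison. State which assays will be run on all FDRs. Use one design label in V.C.6 (case-cohort) and V.F.a (nested case-control).

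The cost is analysis wording and modest extra programming, with no new participants, visits, procedures or assays. The downside is reliance on model adjustment for age and sex instead of matching.

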**III.    Background and Significance**

MS is a progressive, inflammatory and degenerative condition of the CNS with mean clinical onset at age 30^1. MS is the most common CNS inflammatory disorder, with a prevalence of about 1/500 women and 1/1000 men in Colorado. It is a major cause of disability in young adults, and financial and psychosocial costs to the patient and society are great. Diagnosis remains challenging, as early symptoms may be vague and transient, and there is no highly sensitive and specific biomarker or diagnostic test. But there are now 15 disease modifying therapies (DMTs) available, all of which are most effective in those who are younger and relatively newly diagnosed. Delays in treatment are associated with greater accumulation of clinical symptoms and magnetic resonance imaging (MRI) scan abnormalities. Thus, there is a substantial need to develop early detection techniques for MS, so as to treat as early as possible.

But what is early? While clinical symptoms are the first overt indication of MS, evidence is rapidly expanding that there is a prodrome, or pre-clinical phase, prior to first symptoms and then diagnosis of MS. A clinical prodrome may be defined as the time between the onset of decline in a baseline level of functioning until formal diagnostic criteria are met. In the Nurses Health Studies I and II, the 341 women diagnosed with MS after entry into the study had lower levels of physical activity four to six years prior to MS diagnosis compared to age-matched control women. This prodromal period may be associated with

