The preponderance of evidence is consistent with the concept that MS results from the imposition of one or more environmental insults in individuals with a genetic background that predisposes them to MS. Epidemiological studies have identified both genetic (over 200 genes have been identified) and environmental risk factors (exposure to Epstein-Barr virus, obesity, vitamin D deficiency, and smoking) associated with the development of MS, and/or more progressive disease over time, but the triggers at onset remain unknown. Finally, asymptomatic individuals with parents or siblings with MS (first degree relatives - FDRs), have a 10-20 fold increased lifetime risk of developing MS compared to those without a relative with MS. This translates to about 4-5% of girls/women and 2-3% of boys/men who might be ultimately diagnosed with MS in their lifetimes. Diagnosis in multiple family members enhances this risk further. In addition, a variety of cross-sectional MRI studies have identified that about 10% of asymptomatic FDRs of MS patients have brain MRI lesions that could be demyelinating in nature, including fulfilling criteria for lesions disseminated in space (DIS). Thus, given that the median age of onset of relapsing MS is about 30 in multiple studies, we might expect that by age 30, 2-5% of FDR might have developed MS, but up to 5-10% may have developed MRI signs that place them at risk of developing MS, i.e. RIS.

In the recent Genes and Environment in Multiple Sclerosis (GEMS) study of 65 female FDRs of MS patients, those with a combined genetic (based on 64 known single nucleotide polymorphisms, SNPs, in 2012) and environmental (female sex, prior history of mononucleosis and smoking) high risk score were compared to FDRs with a lower score for developing MS. Those with a high risk score showed a trend toward higher BMI and weight, but there were no differences in age, height, cigarette smoking exposure,

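### As written, the Aim 2 risk score is derived from age- and sex-matched sets, so it yields no sex or age main effect and no absolute DIS risk

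*Combined protocol and SAP*

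**What the plan says.** Section V.F, item a, sets up a case-control study nested in the FDR cohort. On the number of cases: "we estimate that 5-10% of the 300 FDRs (15-30) in our pilot study will exhibit an MRI endpoint". On controls: "We will match two controls per case based on age and sex". One control is an FDR without DIS; the other is a non-FDR who has no MRI. Sections V.B and V.C (item 5) describe the same matching. Section V.C (item 6) calls the analysis case-cohort but keeps these controls.

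Section V.F, item c, gives the Aim 2 analysis set as "an estimated case sample size of 30 with 60 age- and sex-matched controls". The score follows from these comparisons by combining the factors that discriminate. The examples are vitamin D, smoking, obesity, NfL, B cell anergy and HLA type; sex and age are not among them. On content, item c says "we plan to use the known risk factors, and add potential biomarkers", and its power calculation assumes that "no single marker would exhibit an odds ratio greater than 2 for increased risk of DIS".

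Section II (Aim 2) asks for a score that takes in every relevant marker of DIS risk. Section III lists female sex as a component of the score in the earlier GEMS study of FDRs, and V.F.c says participants there were grouped "based on a deep phenotyping of 64 SNPs, and environmental screen (including sex"). Section III also gives rates by sex: "This translates to about 4-5% of girls/women and 2-3% of boys/men who might be ultimately diagnosed with MS in their lifetimes", and, for the general population, MS "with a prevalence of about 1/500 women and 1/1000 men in Colorado".

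The plan describes no Aim 2 analysis of all 300 FDRs, no sampling weights, and no baseline rate for the score.

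**The concern.** Matching is a sound way to compare markers between cases and controls. It does not suit a score meant to rank people by risk, because a variable used for matching loses its own association with the outcome within the matched set. A score built only from that set gives the same value to a woman and a man, or to a younger and an older FDR, who have the same markers, whatever the true difference in DIS risk.

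The same set has no baseline. The share of cases in it is chosen by design, so the score gives relative odds and not a probability of DIS. Section I wants an algorithm that separates high-risk from low-risk relatives. The pilot is also meant as groundwork for larger studies, so the omission could carry forward. The plan's admission that it is underpowered does not cover this: larger matched sets would leave it unchanged.

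**Working it through.** **The plan's own figures.** V.F.c states power of 20-33% for ordinary factors and 64% for HLA (odds ratio 2.9) with 30 cases and 60 controls. It gives neither the exposure frequency in controls nor alpha. Assuming an unmatched two-sided 0.05 test, odds ratio 2 gives 21.2% power at a control frequency of 10% and 32.9% at 30%. Odds ratio 2.9 gives 64.2% at a control frequency of 28%. The stated powers are attainable and are not in question here.

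**What matching does to sex.** Suppose 19 of 30 cases are women (about 63%, for illustration). The 60 sex-matched controls are then 38 women and 22 men. Odds ratio = (19 × 22)/(11 × 38) = 418/418 = 1. Any other split also gives 1, as does any multiple of controls. Age behaves in the same way, up to the closeness of the match. Sex-by-marker interactions remain estimable.

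**What it does to the baseline.** Cases are 30/90 = 33% of the whole set and 30/60 = 50% of its FDRs, against an expected 5-10% in the cohort.

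**How strong sex might be, from Section III.** Odds ratio = [pw/(1 − pw)]/[pm/(1 − pm)].

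| Source | Women | Men | Odds ratio |
|---|---|---|---|
| Lifetime MS in FDRs, midpoints | 4.5% | 2.5% | 1.84 |
| Smallest contrast | 4% | 3% | 1.35 |
| Largest contrast | 5% | 2% | 2.58 |
| General-population prevalence | 1/500 | 1/1000 | 2.00 |

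These rates concern MS, as does the maximum odds ratio of 2-3 that V.F.c quotes for known factors. The documents give no DIS rate by sex and no rate of any kind by age.

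**What the full cohort could recover.** Assumptions: 300 FDRs, 150 of them women, sex odds ratio 1.84 for DIS, two-sided 0.05. Power = Φ[(d − 1.96·se0)/se1], where d is the difference in DIS rate and se0 and se1 are its standard errors under the null and the alternative.

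- At 10% DIS, women are 63.4% of cases. The rates are 0.634 × 0.10/0.5 = 12.68% in women and 0.366 × 0.10/0.5 = 7.32% in men, so d = 0.0536. With se0 = √(0.10 × 0.90 × 2/150) = 0.0346 and se1 = 0.0345, power = Φ(−0.41) = 34%.
- At 5% DIS, women are 64.1% of cases. The rates are 6.41% and 3.59%, so d = 0.0282. With se0 = 0.0252 and se1 = 0.0251, power = Φ(−0.84) = 20%.
- Over odds ratios 1.35-2.58 and 50-70% women (assumed), power is 9-65% at 10% DIS and 6-39% at 5% DIS.
- At 10% DIS, women are 63.4% of cases and 48.5% of non-cases. Sex alone then has an AUC of 0.5 + (0.634 − 0.485)/2 = about 0.57, against 0.50 in the matched set by construction.

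**The case against.** The strongest reply is that nothing is lost for good. The cases and FDR controls sit inside a cohort of 300 who all have an MRI and the visit 1 measures; the list of score factors is given only as examples; and Section III (Innovation, item d) compares FDRs with and without MRI abnormalities without mentioning matching. This stands against the stronger reading that the study is unable to put sex or age into a score. The limit applies to the analysis as described, and the plan never says that sex and age are excluded. But it describes no other route to the score.

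A second reply concerns size, and it also stands. The sex rates are lifetime risks of MS diagnosis, whereas the score predicts an MRI finding at ages 18 to 30. A reader might infer that sex is as strong a predictor of DIS as any planned marker, or that the score would misrank women against men by a known amount. The documents do not support either: they give no DIS rate by sex, and even the borrowed odds ratio falls to 1.35 at its low end. For age, Section V.B explains only why the band does not start lower. It shows no gradient within 18-30.

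Third, the earlier study's analysed sample was women only, so sex separated no one there, and that precedent is weak. Fourth, Aim 1 will give overall DIS prevalence. That could anchor a baseline, but the plan does not link it to the score, and it promises only descriptive statistics, not a breakdown by age and sex.

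Finally, age and sex matching is a standard choice for isolating new markers in a proof-of-concept study. That is right for the association tests, and is why the matched set should stay for them.

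**Conclusion.** The concern holds in a limited form. Followed as written, Aim 2 derives its score from a set in which the main effects of sex and age are null by design and absolute risk is undefined. That falls short of Aim 2's own scope, and a better score is available from data the study already collects.

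The fact that these effects are not estimable rests on the design alone and needs no numerical assumption. The size of the loss does need one: an odds ratio of about 1.8 for sex (1.35 to 2.6) applies to lifetime MS, and its transfer to DIS is assumed. No size can be given for age. Nothing here shows the marker comparisons or the stated powers to be wrong. The change should be made, but the expected gain in discrimination from sex alone is modest (AUC about 0.57 under the assumptions above).

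**What to change.** Amend V.F.c as follows.

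1. Keep the matched set for marker association tests and for the visit 2 assays.
2. Fit the risk score in FDRs only, in one model that holds sex, age and markers together. Adding matched-set marker odds ratios to a separate sex-and-age model would count twice any marker that differs by sex, and would use a baseline averaged over marker levels.
3. Use all 300 FDRs for variables held on everyone: smoking, BMI, the questionnaires, and visit 1 blood markers where assayed.
4. For markers measured only in the subset, such as B cell anergy, use FDR cases and FDR controls, with each control weighted by the inverse of its age-by-sex sampling fraction. The average weight would be about 270/30 = 9 with 30 cases and 285/15 = 19 with 15. Ages 18-30 by sex make 13 × 2 = 26 single-year cells, which 15 cases cannot fill, so the weights need broader age bands, set in advance.
5. Leave the non-FDR controls out of the score and the baseline. They have no MRI and lie outside the cohort.
6. Report absolute DIS risk by sex and age with confidence intervals, and specify the age-by-sex table of DIS under Aim 1.

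The cost is a paragraph of text and a record of how many DIS-negative FDRs were eligible as controls in each cell. No new visit or MRI is needed. The downside is imprecision: with 15-30 cases, power for sex is about 20-34% if the odds ratio is 1.84 and half are women, much like the 20-33% the plan accepts for other factors. Few terms can be fitted without shrinkage, so the plan should limit the terms or name a shrinkage method.
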